Title: Functional Genetic Variants Affecting Tacrolimus Trough

Levels and Side Effects in Chinese Renal Transplantation.

ClinicalTrials.gov ID: NCT03083769 Date: Sep. 23, 2019

Study Protocol and Statistical Analysis Plan

Study Protocol:

Aim: Renal transplant is the treatment of choice for patients with end-stage renal disease. Immunological rejection is the leading cause of renal allograft dysfunction after transplant, and immunosuppressant play the main role in preventing against it. Tacrolimus (TAC) has become the main immunosuppressant as it can effectively improve allograft survival and prevent acute rejection. The therapeutic range for TAC is narrow, underexposure to TAC may lead to acute rejection in transplant recipients, whereas overexposure to TAC puts patients at risk of TAC-related side effects including nephrotoxicity, neurotoxicity. Clinical factors and genetic factors play the main role in the variation in TAC trough blood concentrations. There is a necessity for searching genetic marker affecting TAC metabolism and side effects to guide individualized administration of TAC.

Methods: Two cohorts will be enrolled in our study. The Chinese renal transplant recipients recruited at Nanfang Hospital will be set as the Discovery cohort. The Chinese renal recipients recruited at Guilin No. 924 Hospital will be set as Replication cohort. In order to identify the genetic variants accounted for the unexplained variability of TAC and the variants associated with the side effects in Chinese kidney transplant recipients, we will conduct a systematic candidate-SNP approach to investigate the effect of genetic polymorphisms on TAC trough blood concentration and side effects in two Chinese kidney transplant cohorts. The SNPs from two GWAS cohorts, eQTLs from GTEx database, SNPs locating at the promoters of *CYP3A4*, *CYP3A5* and *CYP3A7* gene, and genetic variants previously reported to be associated with variation in TAC trough blood concentration will be analyzed in this study. Additionally, the molecular mechanisms of the novel functional genetic variants will be evaluated, and the impact of clinical factors on TAC trough blood concentrations will be also analyzed.

Statistical Analysis Plan:

Statistical analyses will be performed using software R3.4.1 (R foundation for statistical computing, http://www.r-project.org) and GraphPad Prism5 (https://www.graphpad.com/). The dose-adjusted tacrolimus C_0/D without normal distribution will be log-transformed to attain normality. Multivariate linear regression model will be used to evaluate the association between TAC log(C_0/D) and clinical factors. In Discovery cohort, association analysis between candidate SNPs and TAC log(C_0/D) as well as the risk of acute rejection will be performed in five genetic models using software R 3.4.1 with SNPassoc package. An acute rejection free survival rates

among different genotypes will be calculated using the Kaplan-Meier method. In Replication cohort, SNPassoc package was used to evaluate the association between functional SNPs and TAC $\log(C_0/D)$, as well as the association between functional SNPs and the risk of acute rejection. A two-sided p value<0.05 was considered statistically significant.

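### The regression of log(C0/D) on clinical factors names no genotype term, so factors unrelated to genotype are estimated less precisely than they could be, and any factor related to genotype would be confounded

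*Combined protocol and SAP*

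**What the plan says.** The Aim section of the Study Protocol states that "Clinical factors and genetic factors play the main role in the variation in TAC trough blood concentrations". The Methods section makes the clinical side a declared output, as an additional item: "the impact of clinical factors on TAC trough blood concentrations will be also analyzed". The same section lists the SNP sources, among them promoter SNPs of CYP3A4, CYP3A5 and CYP3A7, and says that "genetic variants previously reported to be associated with variation in TAC trough blood concentration will be analyzed in this study".

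The Statistical Analysis Plan fixes the outcome scale ("The dose-adjusted tacrolimus C_0/D without normal distribution will be log-transformed to attain normality") and then gives the clinical-factor model in one sentence: "Multivariate linear regression model will be used to evaluate the association between TAC log(C_0/D) and clinical factors". It does not list the clinical factors, does not say in which cohort the model is fitted, and does not say whether genotype enters it. Genotype appears only in a separate step for the Discovery cohort, where "association analysis between candidate SNPs and TAC log(C_0/D) as well as the risk of acute rejection will be performed in five genetic models", and in a corresponding step for the Replication cohort. No model containing both clinical factors and genotype is described.

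**The concern.** The plan treats two groups of variables as the main drivers of one outcome, measures both, and then describes a regression on one group only. In linear regression this can have two effects.

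- **Precision.** Variation due to genotype stays in the residual. A clinical factor unrelated to genotype keeps an unbiased coefficient, but its confidence interval is wider than the data require and its test is weaker.
- **Confounding.** If a clinical factor is more common in one genotype group than in another, its coefficient absorbs part of the genotype effect.

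The result at stake is the reported impact of clinical factors on dose-adjusted trough level. Because the sentence is silent on covariates, the analyst could also choose between a model with genotype and one without after seeing both sets of results.

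**Working it through.** The documents give no sample size, SD, effect size or R² for this model, so there is no figure of theirs to reproduce. All numerical inputs below are assumptions, shown with a range.

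**Assumed inputs.** One binary genotype with carrier share p = 0.5; its effect on log(C0/D) is b = −0.5 (range −0.3 to −0.7); residual SD is 0.4 (variance 0.16).

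**1. Precision, factor unrelated to genotype.** Here R² = b²p(1−p) / [b²p(1−p) + 0.16], and the standard error with genotype divided by that without is √(1−R²).

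| b | R² | √(1−R²) | SE shorter by |
|---|---|---|---|
| −0.3 | 0.0225/0.1825 = 0.12 | 0.94 | 6% |
| −0.5 | 0.0625/0.2225 = 0.28 | 0.85 | 15% |
| −0.7 | 0.1225/0.2825 = 0.43 | 0.75 | 25% |

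In terms of power at the SAP's two-sided 0.05 level, take a factor with 80% power when genotype is included. Without genotype its power is Φ[(1.96 + 0.84)√(1−R²) − 1.96], which gives 76%, 65% and 51% at R² = 0.10, 0.30 and 0.50.

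**2. Confounding, factor related to genotype.** The bias from omission is b × [P(carrier | factor present) − P(carrier | factor absent)]. Suppose a binary factor has a true effect of +0.30 and is present in 20% of non-carriers.

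- Present in 20% of carriers: the difference is 0 and there is no bias.
- Present in 35% of carriers: 0.35/0.55 − 0.65/1.45 = 0.636 − 0.448 = 0.188. The bias is −0.5 × 0.188 = −0.094 and the estimate is +0.21 (range +0.24 to +0.17).
- Present in 50% of carriers: 0.50/0.70 − 0.50/1.30 = 0.714 − 0.385 = 0.330. The bias is −0.165 and the estimate is +0.14 (range +0.20 to +0.07).

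**3. Is precision always lost?** No. Let c² be the squared correlation of factor and genotype, and f = R²/(1−R²), with R² the value that would hold at c² = 0. Then SE(without)/SE(with) = √{[1 + f(1−c²)](1−c²)}. With R² = 0.10 and the factor present in 20% against 60%, c² = 0.167 and f = 0.111. The ratio is √(1.093 × 0.833) = 0.95. The standard error is then smaller without genotype, around a biased estimate.

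**4. Does adding genotype always remove the bias?** No. Suppose the factor is a response to an earlier tacrolimus level. I simulated 400,000 patients with b = −0.5, residual SD 0.4 and a true effect of +0.30. The factor was given to 80% of those in the lowest 30% of an earlier level and to nobody else. With genotype in the model, the estimate was +0.30, +0.01 or −0.29 when the residuals of the earlier and later levels were correlated 0, 0.5 or 1. Genotype adjustment is sufficient only when nothing but genotype links the two levels.

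**The case against.** The strongest reply has three parts.

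- **Silence is not exclusion.** The SAP is one paragraph and does not rule genotype out. This stands: the accurate statement is that the model names no genotype term. The plan as written nevertheless leads to a clinical-only model, since genotype is placed in a different analysis and no joint model is described.
- **A clinical-only model can be legitimate.** The SAP speaks of association, and the Methods aim at variability not yet explained, so the regression could serve as a baseline for the genetic work. The documents do not state that purpose, and they do not contradict it. Showing the clinical-only model next to the adjusted one preserves this use.
- **The aim is additional.** This also stands and limits the weight of the point, because this model is not the SNP association test.

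A reader might go further and infer that the model covers co-medication prescribed because a patient metabolises tacrolimus fast, so that its effect is certainly biased or even reversed. The documents do not support this. They list no clinical factors, mention no concomitant drugs, and describe no treatment given in response to a level. A reader might also infer that every estimate loses precision. Step 3 of the working shows that this is not general.

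**Conclusion.** The point holds in limited form. The clinical-factor regression leaves out, as written, a determinant that the protocol itself calls a main one and that the study will measure. For factors unrelated to genotype, the result is avoidable imprecision: standard errors are about 6% to 25% shorter with genotype included, if genotype explains 12% to 43% of the variance. That range rests on the assumed effect, carrier share and residual SD, and no figure in the documents confirms it.

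Confounding is a conditional risk. It is zero for any factor independent of genotype. In the assumed examples it takes about 0.09 to 0.17 off a true +0.30 at the central genotype effect. Whether any factor in this study is associated with genotype cannot be told from the documents. For a factor that follows earlier levels, adding genotype may remove all, part or little of the bias. The change is worth making because it is cheap and serves a declared output; the SNP conclusions do not depend on it.

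**What to change.** In the Statistical Analysis Plan:

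1. List the clinical factors in the model.
2. State that the clinical-factor regression of log(C0/D) is fitted in each cohort with the previously reported CYP3A genotypes as fixed covariates. Name them in advance, so that they are not picked from the study's own SNP results.
3. Take the reported clinical-factor effects from that model and show the clinical-only model beside it.
4. Describe the coefficient of any factor that responds to earlier tacrolimus levels as an association only, not as the effect of that factor.

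The cost is a few sentences and one extra model per cohort. A few degrees of freedom are spent, and patients with a missing genotype call drop out of the adjusted model, so the number analysed should be given for both models. One point needs checking: for the Replication cohort the SAP mentions only functional SNPs, so the sponsor should confirm that the chosen CYP3A genotypes are also available there.

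### The SAP states no conditioning on previously reported variants for the SNP tests of log(C0/D), so these tests alone do not show that a SNP explains variability beyond them

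*Combined protocol and SAP*

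**What the plan says.** The Methods paragraph of the Study Protocol gives the purpose as "In order to identify the genetic variants accounted for the unexplained variability of TAC", and in the same sentence the broader task "to investigate the effect of genetic polymorphisms on TAC trough blood concentration and side effects". Its candidate list includes "SNPs locating at the promoters of *CYP3A4*, *CYP3A5* and *CYP3A7* gene", alongside SNPs from genome-wide studies and expression databases. It also says that "genetic variants previously reported to be associated with variation in TAC trough blood concentration will be analyzed in this study". Reported variants are therefore candidates to be tested; no text makes them conditioning terms.

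On TAC levels, the Statistical Analysis Plan contains these pieces:

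- The outcome: "The dose-adjusted tacrolimus C_0/D without normal distribution will be log-transformed to attain normality". Dose is thus already handled in the outcome.
- Clinical factors: "Multivariate linear regression model will be used to evaluate the association between TAC log(C_0/D) and clinical factors". No SNP term is mentioned and no factor is listed.
- Discovery: "association analysis between candidate SNPs and TAC log(C_0/D) as well as the risk of acute rejection will be performed in five genetic models".
- Replication: "In Replication cohort, SNPassoc package was used to evaluate the association between functional SNPs and TAC" log(C0/D). The sentence is in the past tense and names only functional SNPs.
- Significance: two-sided p below 0.05.

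No sentence brings the clinical factors or the reported variants into the SNP tests, fits SNPs jointly, or asks for incremental R². The documents state no sample size, effect size or LD.

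**The concern.** A marginal SNP test measures total association with log(C0/D). The stated purpose is narrower: variability that is not yet explained. In its natural sense this is variability left after known sources, and reported variants are among those.

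If a candidate SNP is correlated with a reported variant that does affect log(C0/D), the candidate inherits part of that association even when it has no effect of its own. Replication does not guard against this, because the same correlation can be present in the second cohort. Followed as written, the plan could credit and replicate a SNP that only tags a variant already reported. Candidates drawn from neighbouring CYP3A genes and pooled with reported variants make such correlation possible, although the documents do not establish it.

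A lesser matter is that the clinical-factor regression is not linked to the SNP tests. Variance that clinical factors could explain then stays in the error term, which costs precision.

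The point concerns log(C0/D) only, not acute rejection.

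**Working it through.** The plan gives no figure to reproduce. Only the two-sided alpha of 0.05 comes from the documents. All other inputs are assumed, so the results show what is possible, not how large the problem is in this trial.

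**1. SNP with no effect of its own, marginal additive test.** Let K be the share of variance in log(C0/D) explained by the reported variant, and r² its LD with the candidate. The candidate's marginal R² is q = K·r². The noncentrality is n·q/(1 − q), referred to F with 1 and n − 2 df.

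For n = 200, K = 0.20, r² = 0.1: q = 0.02, noncentrality = 200 × 0.02/0.98 = 4.08, P(p < 0.05) = 0.520.

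| K | LD r² | n = 100 | n = 200 |
|---|---|---|---|
| any | 0 | 0.050 | 0.050 |
| 0.05 | 0.05 | 0.079 | 0.109 |
| 0.20 | 0.1 | 0.293 | 0.520 |
| 0.20 | 0.2 | 0.524 | 0.819 |

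A simulation (2000 runs, allele frequencies 0.3) at n = 200, K = 0.20, r² = 0.1 gave 0.519 marginally and 0.049 with the reported variant in the model.

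**2. Replication.** With 200 + 100 patients, K = 0.20, r² = 0.1 in both cohorts and every Discovery hit carried forward, the product of powers is 0.520 × 0.293 = 0.152. A simulation requiring the same direction gave 0.158 (4000 runs). At r² = 0, theory gives 0.05 × 0.025 = 0.00125. If a functional screen removes a share s of such SNPs before Replication, multiply by (1 − s).

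**3. Does clinical adjustment cure this?** With clinical factors explaining 20%, the partial R² is 0.02/(1 − 0.2) = 0.025 and the noncentrality is 200 × 0.025/0.975 = 5.13. P(p < 0.05) is 0.615, against 0.520 without adjustment. It does not remove the LD problem.

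**4. When the reported variant only tags the causal one.** Let the reported variant have r² = a, and the candidate r² = b, with a causal variant explaining K = 0.20, linked only through it. The partial correlation is (√(Kb) − √(Ka)·√(ab)) / √((1 − Ka)(1 − ab)), with n − 3 df. For a = 0.8, b = 0.2: (0.2 − 0.4 × 0.4)/√(0.84 × 0.84) = 0.0476, so at n = 200 the noncentrality is 0.455 and P = 0.103.

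| n = 200 | b = 0.2 | b = 0.5 |
|---|---|---|
| marginal | 0.819 | 0.997 |
| conditional, a = 0.5 | 0.350 | 0.788 |
| conditional, a = 0.8 | 0.103 | 0.242 |
| conditional, a = 0.9 | 0.064 | 0.102 |
| conditional, a = 1 | 0.050 | 0.050 |

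**5. Precision from clinical covariates.** For an independent SNP explaining 2%, with covariates explaining C, the partial R² is 0.02/(1 − C). At n = 200, power is 0.520 (C = 0), 0.564 (C = 0.1) and 0.675 (C = 0.3). At n = 100 it is 0.293, 0.320 and 0.397. The unadjusted 0.520 equals the step 1 example because both have R² = 0.02.

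**6. Power cost of conditioning.** For a real own effect of 2% and covariates explaining 30%, the partial R² is 0.02(1 − r²)/0.7. At n = 200, power is 0.675, 0.520, 0.395 and 0.187 at LD r² of 0, 0.3, 0.5 and 0.8. At n = 100 it is 0.397, 0.293, 0.222 and 0.117.

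**The case against.** The strongest reply is that no marginal test, by itself, shows incremental variance, and the SAP never says that p < 0.05 will be read as independence from reported variants. The case rests on one undefined phrase about unexplained variability, in a sentence that also states a broader aim for which marginal tests are adequate. This stands as a limit on weight: what is shown is a stated purpose without an analysis, not an invalid test.

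Second, omitting clinical factors unrelated to genotype costs precision and need not bias the SNP test, and with covariates explaining 10% the gain is small (0.52 to 0.56 at n = 200). Adjusting for a post-transplant factor that is itself affected by genotype or TAC exposure could distort a real effect. Both points stand, so clinical adjustment is secondary and restricted below.

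Third, LD may be zero, and mechanism work may screen out some tagging SNPs. Both are possible. But the documents do not say which candidates are in LD with reported variants, nor whether the mechanism work precedes Replication, and that work does not measure incremental variance.

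A reader might also infer that the SAP declares the tests unadjusted, or that its word novel requires a conditional model. Neither is supported. The text is silent on covariates, so an adjusted model may have been intended; and if novel means only not previously reported, that word needs no conditional model.

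**Conclusion.** The concern holds for log(C0/D) in this form: the plan specifies nothing that measures what a SNP adds to the reported variants, although its purpose clause calls for that. LD with reported variants is the substantive defect; the missing clinical covariates are a matter of efficiency.

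The size for this trial cannot be determined. The 52% figure rests on n = 200, a reported variant explaining 20% and LD r² of 0.1. Across the combinations in step 1 of the working it runs from 5% at r² = 0 to 82%. A reader might infer that most replicated SNPs would be spurious; the documents do not support this, since they give no LD, effect size or sample size, and the two-cohort figure assumes that no functional screen intervenes.

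The plan should be changed, but a limit on the claims would suffice if no claim of independence is intended. Confidence is medium.

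**What to change.** **Main change, for log(C0/D).**

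- For each non-reported SNP put forward, add one prespecified genetic model (for example additive) that includes the genotyped reported variants. Choose these by an LD or distance rule, with a rule for dropping collinear ones, both fixed before the SNP results are seen.
- Report incremental R² beside the marginal result.
- Use the wording *independent of the genotyped reported variants* only on that result. Read failure as *not shown to be independent*, not as absence of function.
- In Replication, do the same where the reported variants are genotyped. Otherwise limit the claim to replicated marginal association. If those data were already analysed, as the past tense may suggest, label the model post hoc.
- If no claim of independence is intended, say so and define novel as not previously reported.

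**Secondary change, for precision only.** Include in the SNP models a clinical covariate set fixed in advance and restricted to factors not affected by genotype or TAC exposure.

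**Cost.** In Discovery this is mainly SAP wording, using factors and variants already planned for analysis. In Replication it may need extra genotyping or a narrower claim. Statistically it costs a few degrees of freedom and power for real variants in strong LD with a reported one (assumed example, n = 200: 0.68 at r² 0, 0.19 at r² 0.8). Residual association can remain when the reported variant only tags the causal one, which is why the claim names the genotyped variants.

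### Does the lack of a stated follow-up period for the SNP–acute rejection tests call for a change to the plan?

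*Combined protocol and SAP*

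**What the plan says.** Under Statistical Analysis Plan, the Discovery analysis relates candidate SNPs to log(C0/D) "as well as the risk of acute rejection will be performed in five genetic models using software R 3.4.1 with SNPassoc package". Rejection-free survival "among different genotypes will be calculated using the Kaplan-Meier method". In the Replication cohort the plan evaluates functional SNPs against log(C0/D), "as well as the association between functional SNPs and the risk of acute rejection". One rule covers everything: "A two-sided p value<0.05 was considered statistically significant".

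No sentence gives a time origin, a horizon, a minimum observation time or a censoring rule for rejection. None names an outcome model, an effect measure or covariates for it. The Study Protocol does not fill the gap. Its Aim mentions rejection as background ("underexposure to TAC may lead to acute rejection in transplant recipients"). Its Methods state the objective as to "investigate the effect of genetic polymorphisms on TAC trough blood concentration and side effects in two Chinese kidney transplant cohorts". The cohorts are defined by hospital ("Two cohorts will be enrolled in our study"), with no observation window.

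**The concern.** Whether a patient counts as a rejection case depends on how long that patient is watched. If the plan is silent, analyses at 6 months, at 1 year and over all follow-up can each be said to comply. They use different event counts, so a SNP may fall below 0.05 in one and not in another. Nothing in the text obliges Replication to use the period chosen in Discovery. If the choice often settled the result, a reader could not tell whether a SNP reported as associated, or as replicated, owed that status to the period.

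**Working it through.** **Inputs.** The documents supply one number, the two-sided level of 0.05. They give no sample size, rejection rate, allele frequency, effect size or follow-up, so there is no figure of the plan's to reproduce. Everything else is assumed: 250 patients per cohort, allele frequency 0.3, 15% rejection by 1 year, Weibull times with shape 0.6, follow-up uniform between 1 and 5 years, additive coding, and a binary likelihood-ratio test. Mean events at hazard ratio 1.8 are 26 by 6 months, 38 by 1 year and 65 over all follow-up.

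**Error rate.** For null SNPs each single-period test rejects 5.0–5.8% of the time. Tests at 1 year and over all follow-up disagree for 7.3% of null SNPs, and about 20% of those significant in either period are significant in both. That overlap is what two correlated tests near 5% produce. With 5.5% each, both = (5.5 + 5.5 − 7.3)/2 = 1.85%, either = (5.5 + 5.5 + 7.3)/2 = 9.15%, and 1.85/9.15 = 20%. It is not a sign of inflation.

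**Splitting the disagreement.** Let *a* be the share of SNPs significant only over all follow-up and *b* the share significant only at 1 year. Then *a* + *b* is the disagreement and *a* − *b* is the difference in power. All figures are percentages.

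| True effect | Power, 1 year | Power, all | *a* − *b* | *a* + *b* | *a* | *b* |
|---|---|---|---|---|---|---|
| HR 1.8, lasting | 69.0 | 88.4 | 19.4 | 23.9 | 21.65 | 2.25 |
| HR 1.5, lasting | 38.0 | 56.6 | 18.6 | 28.4 | 23.5 | 4.9 |
| HR 1.8, first 6 months only | 45.1 | 29.2 | −15.9 | 24.5 | 4.3 | 20.2 |

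For 6 months against all follow-up at a lasting hazard ratio of 1.8, power is 52.7% and 88.4%, and the disagreement is 39.3%. Hence *a* = (39.3 + 35.7)/2 = 37.5 and *b* = 1.8.

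With a lasting effect, nearly all the disagreement runs one way: the longer period has more events and finds more. The two estimates differed in sign in only about 1% of disagreeing pairs (1 year against all) and 3% (6 months against all). These are differences in precision, not contradictory findings.

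**Dependence on the assumptions.** Shape 0.6 makes the cumulative hazard at 3 years 3^0.6 = 1.93 times its 1-year value. If that ratio is 1.30 (shape 0.24, since 3^0.24 = 1.30), disagreement between 1 year and all follow-up falls to 15.5% at hazard ratio 1.8 and 17% at 1.5. Disagreement between 6 months and all follow-up falls to about 22% for both. In the base case at hazard ratio 2.5, 1 year against all follow-up gives 3%. With 500 patients, a 20% rate and hazard ratio 2.0 it is below 0.5%.

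A separate simulation used complete follow-up, 3 against 12 months and allele frequency 0.25. It gave 14–26% at hazard ratio 1.5 for 150 to 500 patients and 10–20% rejection, but 5% or less at hazard ratio 2.0 and above with 500 patients and 20% rejection.

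**Would naming a period help?** Power at 6 months, 1 year and all follow-up is 53%, 69% and 88% if hazard ratio 1.8 lasts, but 57%, 45% and 29% if the effect stops at 6 months. The ranking reverses, and the documents give no basis for preferring one case. With the period set to all follow-up, the choice between a binary and a Cox analysis changes significance for only 2–8% of associated SNPs.

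**The case for a change.** The strongest case for a change is that the gap is real and cheap to close. No period is stated for either cohort. Modest effects with few events are a plausible setting for a study of this kind. There, a disagreement of 15–29% between 1 year and all follow-up is not trivial, and the reversal under an early-only effect means no default is safe. A sentence fixing one period for both cohorts would cost wording only.

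The factual part stands, and so do the base-case figures, which came out close to these values when recalculated. Three parts do not carry the weight put on them.

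- First, multiplying powers across cohorts (for example 0.690 × 0.690 = 0.48 at 1 year against 0.884 × 0.884 = 0.78 over all follow-up) supposes that a rejection p-value below 0.05 admits a SNP to Replication. The plan sends functional SNPs there and states no such rule.
- Second, the headline figures use additive coding alone, whereas Discovery uses five genetic models, so they do not describe the planned procedure.
- Third, it is doubtful that every period complies equally. With no cut-off stated and rejection-free survival estimated by Kaplan-Meier, all available follow-up is the ordinary reading, and a 6-month cut would be an added restriction. The same outcome wording in both cohorts, one of them labelled Replication, also implies a common definition, though it does not say so.

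A log-rank test, or curves in both cohorts, would be a reasonable addition but would correct no wrong result. Descriptive curves are legitimate.

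**Conclusion.** No change to the plan follows. The SAP omits a detail; it does not specify a wrong analysis. Any one period fixed in advance gives a valid test as long as follow-up is unrelated to genotype, and the documents offer no ground for calling one period better than another.

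On assumed inputs, significance differs between 1 year and all follow-up for about 15–29% of SNPs with hazard ratios of 1.5–1.8, chiefly because later events add power when the effect lasts. It differs for about 7% of null SNPs and for 3% or less where effects are larger (hazard ratio 2.5, or 2.0 with 500 patients and a 20% rate). These sizes rest wholly on assumed sample size, rejection rate, allele frequency and timing of rejection, so the documents cannot show which regime applies.

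The reach is also limited. The log(C0/D) analyses, which serve the stated trough-level objective, are untouched. Analysts can fill the gap sensibly by following patients from transplant to first rejection over the available follow-up in both cohorts. A results report would ordinarily say which period was used.
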